**Table 2 Schedule of assessments for patients who have discontinued all study treatment**

Evaluation	Time since last dose of IP								For details, see Section
	Day ( $\pm 3$ )	Months ( $\pm 1$ week)						12 months and every 2 months thereafter ( $\pm 2$ weeks)	
	30	2	3	4	6	8	10		
Physical examination (full)	X								8.2.2
Vital signs (temperature, respiratory rate, blood pressure, and pulse)	X								8.2.3
Weight	X	X	X		X				8.2.3
Pregnancy test a	X	As clinically indicated							5.1
AE/SAE assessment	X	X	X						8.3
Concomitant medications	X	X	X						6.6
WHO/ECOG performance status	At timepoints consistent with tumor assessments; at 30, 60, and 90 days; and then at initiation of subsequent anticancer therapy b								8.2.5
Subsequent anticancer therapy c	<----->								8.1
Survival status d		X	X	X	X	X	X	X (every 2 months)	8.1
Hematology	X	X	X						Table 10
Clinical chemistry	X	X	X						Table 9
Urinalysis e	As clinically indicated								Table 11
TSH (reflex free T3 or free T4) f	X	X	X						Table 9
Durvalumab PK sample (serum) g			X						8.5.1.1
Olaparib PK sample (plasma)	X								8.5.1.2
Immunogenicity assessment (ADA sampling) to identify ADA responses g			X		X				8.5.2
Whole blood – exploratory analysis (mandatory) h			X						8.8.1.3

**Table 2 Schedule of assessments for patients who have discontinued all study treatment**

Evaluation	Time since last dose of IP							12 months and every 2 months thereafter (±2 weeks)	For details, see Section
	Day (±3)	Months (±1 week)							
	30	2	3	4	6	8	10		
EORTC QLQ-C30 and EQ-5D-5L i	X	X	X	Patients who enter follow-up without PD and do not attain PD by follow-up Month 3 will continue with q8w (±7 days relative to follow-up Month 3 visit date) until PD and thereafter complete 1 more assessment. Patients who attain PD by follow-up Month 3 will complete only 1 additional q8w assessment.				8.1.4.1, 8.1.4.2	
Tumor assessment (CT or MRI) (RECIST 1.1) j	q8w ±1 week beginning 8 weeks after randomization for the first 48 weeks, and then q12w ±1 week thereafter (relative to the date of randomization) until clinical progression with or without RECIST 1.1-defined radiological progression. An additional follow-up scan is requested, if clinically feasible. The schedule of q8w ±1 week for the first 48 weeks and then q12w ±1 week thereafter MUST be followed regardless of any delays in dosing.							8.1	

- a For women of childbearing potential only. A urine or serum pregnancy test is acceptable.
- b WHO/ECOG performance status should also be collected at other site visits that the patient attends; if appropriate, site staff are available to collect such information. In addition, WHO/ECOG performance status should be provided when information on subsequent anticancer therapy is provided, where possible.
- c Details of any treatment for UC after the last dose of the IP must be recorded in the eCRF. At minimum, collect the start date and description of the subsequent anticancer therapy.
- d Patients may be contacted in the week following data cutoffs to confirm survival status. Details of any treatment for UC after the last dose of the IP must be recorded in the eCRF.
- e Individual sites are required to indicate in the eCRF if a urinalysis was performed during an unscheduled visit.
- f Free T3 or free T4 will only be measured if TSH is abnormal or if there is clinical suspicion of an AE related to the endocrine system.
- g PK and immunogenicity samples for durvalumab are collected 90 days (3 months; ±7 days) after treatment with durvalumab ends. In addition, a final sample for ADA is taken 6 months (±7 days) after treatment with durvalumab ends.
- h Whole blood for exploratory analyses will be collected during screening, pre-dose on Day 1 of Cycles 1 to 4, every 12 weeks thereafter (ie, every 3 cycles), at discontinuation/progression (Table 1), and at the 90-day follow-up visit.
- i PRO assessments will be done using a site-based electronic device. It is preferred that PRO questionnaires are completed prior to any other study procedures and before discussion of disease progression to avoid biasing the patient’s responses to the questions.

- j Patients will have on-study scans done q8w  $\pm$ 1 week for the first 48 weeks relative to the date of randomization and then q12w  $\pm$ 1 week thereafter until clinical progression with or without RECIST 1.1-defined radiological progression. An additional follow-up scan is requested, if clinically feasible. Clinically stable patients with RECIST 1.1-defined radiological PD who continue to receive study treatment at the discretion of the Investigator and patient (following consultation with AstraZeneca) should receive a subsequent scan, preferably at the next regularly scheduled imaging visit but no earlier than 4 weeks later, and this subsequent scan is assessed using the Confirmation of Radiological Progression criteria described in [Appendix F](#). RECIST 1.1 assessments will be performed on images from CT (preferred) or MRI, each preferably with IV contrast of the chest, abdomen, and pelvis. Additional anatomy should be imaged based on signs and symptoms of individual patients at baseline and follow-up. If an unscheduled assessment was performed and the patient has not progressed, every attempt should be made to perform the subsequent assessment at their next scheduled visit.

ADA Antidrug antibody; AE Adverse event; CT Computerized tomography; ctDNA circulating tumor deoxyribonucleic acid; ECOG Eastern Cooperative Oncology Group; eCRF Electronic case report form; EORTC QLQ-C30 European Organisation for Research and Treatment of Cancer 30-item core quality of life questionnaire; EQ-5D-5L EuroQoL 5-dimension, 5-level health state utility index; IP Investigational product; IV Intravenous; MRI Magnetic resonance imaging; PD Progressive disease; PK Pharmacokinetics; PRO Patient-reported outcome; q4w Every 4 weeks; q8w Every 8 weeks; q12w Every 12 weeks; RECIST 1.1 Response Evaluation Criteria in Solid Tumors, version 1.1; SAE Serious adverse event; T3 Triiodothyronine; T4 Thyroxine; TSH Thyroid stimulating hormone; UC Urothelial cancer; WHO World Health Organization.

### Rationale:

Treatment options for platinum-ineligible patients with urothelial cancer (UC) remain limited with relatively low objective response rate (ORR) with monotherapy programmed cell death 1 (PD-1) or programmed cell death ligand 1 (PD-L1) therapy. Olaparib will be combined with the PD-L1 inhibitor durvalumab to broaden the therapeutic effect of durvalumab monotherapy, based in part on the separate non-overlapping mechanisms of action of the component agents and on the potential for mechanistic synergy. Based on this biology, the hypothesis to be tested in this study is that increased DNA damage triggered through poly (ADP ribose) polymerization (PARP) inhibition will result in enhanced antitumor immunity that can be further enhanced through combination with an immune checkpoint inhibitor in UC. It is also anticipated that the combination of olaparib and durvalumab will be of particular benefit to patients with metastatic UC with DNA repair-deficient cancers (as assessed by presence of inactivating mutations in homologous recombination repair [HRR] genes). However, this mechanism of enhanced PARP inhibitor-induced immune activation may be operative in all patients, and therefore, the study design will be employed to evaluate the safety and efficacy of olaparib and durvalumab in both HRR mutated (HRRm) and HRR wild-type (HRRwt) patients.

## Objectives and endpoints

Primary objective:	Endpoint/Variable:
To assess the efficacy of durvalumab + olaparib combination therapy compared with durvalumab + placebo in terms of PFS	PFS as determined by Investigator assessment according to RECIST 1.1
Secondary objectives:	Endpoint/Variable:
Key secondary objective:	
To assess the efficacy of durvalumab + olaparib combination therapy compared with durvalumab + placebo	OS
Additional secondary objectives:	
To assess the efficacy of durvalumab + olaparib combination therapy compared with durvalumab + placebo	DoR, ORR, and PFS6 according to RECIST 1.1 using Investigator assessment OS18
To assess the efficacy of durvalumab + olaparib combination therapy compared with durvalumab + placebo in the subset of patients with HRRm	PFS, DoR, ORR, and PFS6 according to RECIST 1.1 using Investigator assessment
To assess the PK of durvalumab and olaparib in both treatment arms	Concentration of durvalumab and olaparib
To investigate the immunogenicity of durvalumab in both treatment arms	Presence of ADAs for durvalumab
To assess disease-related symptoms and HRQoL in patients with UC treated with durvalumab + olaparib combination therapy compared with durvalumab + placebo	EORTC QLQ-C30: Global health status/QoL, functioning (physical), and multi-term symptoms (fatigue and pain)
Safety objective:	Endpoint/Variable:
To assess the safety and tolerability profile of durvalumab + olaparib combination therapy compared with durvalumab + placebo	AEs/SAEs, physical examinations, laboratory findings (including clinical chemistry, hematology and urinalysis), WHO/ECOG performance status, and vital signs
Exploratory objectives	Endpoint/Variable:
To assess overall change in health status since the start of study treatment in UC patients treated with durvalumab + olaparib combination therapy compared with durvalumab + placebo	PGIC
To explore the impact of treatment and disease state on health state utility using the EQ-5D-5L during assigned treatment	EQ-5D-5L will be used to derive health state utility based on patient-reported data
To collect blood, urine, and tissue samples for defining biological responses to durvalumab + olaparib and for identifying candidate markers that may correlate with likelihood of clinical benefit	Biomarkers (eg, DNA or ctDNA alterations, protein expression detected by IHC, change in ctDNA levels, and mRNA expression) correlating with clinical response

ADA Anti-drug antibody; AE Adverse event; CR Complete response; ctDNA Circulating tumor deoxyribonucleic acid; DNA Deoxyribonucleic acid; DoR Duration of response; ECG Electrocardiogram; ECOG Eastern Cooperative Oncology Group; EORTC QLQ-C30 European Organisation for Research and Treatment of Cancer 30-item core quality of life questionnaire; EQ-5D-5L EuroQoL 5 dimension, 5-level health state utility index; HRQoL Health-related quality of life; HRRm homologous recombination repair mutated; IHC Immunohistochemistry; mRNA Messenger ribonucleic acid; ORR Objective response rate; OS Overall survival; OS18 Patients alive at 18 months; PD-L1 Programmed death ligand 1; PFS Progression-free survival; PFS6 Progression-free survival at 6 months; PGIC Patient Global Impression of Change; PK Pharmacokinetic(s); PRO Patient-reported outcome; QoL Quality of Life; RECIST 1.1 Response Evaluation Criteria in Solid Tumors, version 1.1; SAE Serious adverse event; UC Urothelial cancer; WHO World Health Organization.

### **Overall design:**

This is a Phase II, randomized, double-blind, placebo-controlled, multi-center, comparative global study to determine the efficacy and safety of durvalumab + olaparib combination therapy versus durvalumab + placebo (durvalumab monotherapy) as first-line treatment in patients ineligible for platinum-based therapy with unresectable Stage IV UC.

### **Study period:**

Estimated date of first patient enrolled: Q1 2018

Estimated date of last patient completed: Q2 2021

### **Number of patients:**

Approximately 150 patients globally will be randomized in a 1:1 ratio to either the durvalumab + olaparib treatment group or the durvalumab + placebo treatment group (75 patients per arm). The randomization will be stratified based on HRR status (mutant versus wild type) and Bajorin risk index (a composite stratum for lymph node only metastasis versus metastasis to any other organ system and Eastern Cooperative Oncology Group [ECOG] performance status [0, 1 versus 2]).

### **Treatments and treatment duration:**

Durvalumab and olaparib/placebo will be administered beginning on Day 1 until confirmed progressive disease (PD) as per RECIST 1.1 as assessed by the Investigator unless there is unacceptable toxicity, withdrawal of consent, or another discontinuation criterion is met.

### **Progression during treatment**

During the treatment period, patients receiving durvalumab + olaparib or durvalumab + placebo who are clinically stable at an initial RECIST 1.1-defined PD may continue to receive study treatment at the discretion of the Investigator and patient. A follow-up scan is to be collected after the initial RECIST 1.1-defined PD, preferably at the next (and no later than the next) scheduled imaging visit and no less than 4 weeks after the prior assessment of PD, and this scan is evaluated using the Confirmation of Radiological Progression criteria, which are outlined in [Appendix F](#). If the subsequent scan does not confirm the immediate prior radiological PD, scanning should continue until the next RECIST 1.1-defined PD, which in turn will require a subsequent scan evaluated using the Confirmation of Radiological

Progression criteria outlined in [Appendix F](#). However, patients in the immunotherapy arm(s) will not be permitted to continue immunotherapy if progression occurs after confirmed response (complete response or partial response as defined by RECIST 1.1) to immunotherapy treatment in the target lesions (regardless of the appearance of new lesions) (ie, the response and progression events both occurred in the target lesions while receiving immunotherapy during the same treatment period).

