#### **4.2.3 Rationale for treatment duration**

Treatment in this study will continue until RECIST 1.1-defined PD and Investigator determination that the patient is no longer benefiting from treatment with the investigational product (IP) or until another discontinuation criterion is met (see Section 7.1).

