**Table 5 Study treatments**

	Durvalumab	Olaparib	Placebo
Dosing instructions b	1500 mg IV q4w c	300 mg BID administered to patients with CrCl $\geq$ 51 mL/min; 200 mg BID will be administered to patients with CrCl $\geq$ 31 mL/min but $<$ 51 mL/min	Matching placebo for oral tablet BID
Packaging and labeling	Provided in 500-mg vials, labeled in accordance with GMP Annex 13 and per country regulatory requirements d	Labels will be prepared in accordance with GMP and local regulatory guidelines. The labels will fulfil GMP Annex 13 requirements for labeling. Label text will be translated into local language.	Labels will be prepared in accordance with GMP and local regulatory guidelines. The labels will fulfil GMP Annex 13 requirements for labeling. Label text will be translated into local language.
Provider	AstraZeneca	AstraZeneca	AstraZeneca

a Refer to Section 6.3 for detailed formulation and preparation instructions for IPs.

b Detailed instructions for IP administration are provided below. Refer to Section 6.2 for details on duration of treatment and criteria for treatment through progression (Appendix F).

c If a patient's weight falls to  $\leq$ 30 kg or below, the patient should receive weight-based dosing equivalent to 20 mg/kg of durvalumab q4w until the weight improves to  $>$ 30 kg, at which point the patient should start receiving the fixed dosing of durvalumab 1500 mg q4w.

d Label text will show the product name as "MEDI4736" or "durvalumab (MEDI4736)" depending on the agreed product name used in the approved study master label document. All naming conventions are correct during this transitional period.

BID Twice a day; CrCl Creatinine clearance; GMP Good Manufacturing Practice; IV Intravenous; q4w Every 4 weeks.

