## **6.2 Duration of treatment and criteria for treatment through progression**

Durvalumab and olaparib/placebo will be administered beginning on Day 1 until confirmed PD as per RECIST 1.1 as assessed by the Investigator unless there is unacceptable toxicity, withdrawal of consent, or another discontinuation criterion is met.

Patients with rapid tumor progression or with symptomatic progression that requires urgent medical intervention (eg, central nervous system metastasis, respiratory failure due to tumor compression, and spinal cord compression) will not be eligible for continuing durvalumab or olaparib/placebo. For all patients who are treated through progression, the Investigator should ensure that patients do

not have any significant, unacceptable, or irreversible toxicities that indicate that continuing treatment would not further benefit the patient.

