### **Confirmation of Radiological Progression**

Patients who are clinically stable at an initial RECIST 1.1-defined PD may continue to receive treatment at the discretion of the Investigator and patient. A follow-up scan is collected after the initial RECIST 1.1-defined PD, preferably at the next (and no later than the next) scheduled imaging visit, and no less than 4 weeks after the prior assessment of PD and the Confirmation of Radiological Progression criteria described below are applied as tumor assessments for this follow-up scan.

For all patients who are treated through progression, the Investigator should ensure that the patient does not have any significant, unacceptable, or irreversible toxicities that indicate that continuing treatment will not further benefit the patient.

The criteria for continuing treatment despite RECIST 1.1-defined progression are as follows:

- There is absence of clinical symptoms or signs indicating clinically significant disease progression accompanied by a decline in WHO/ECOG performance status >1.
- There is absence of rapid disease progression or threat to vital organs or critical anatomical sites (eg, central nervous system metastasis, respiratory failure due to tumor compression, or spinal cord compression) requiring urgent alternative medical intervention. Concurrent radiation treatment is not permitted. If a patient requires palliative radiation or prophylactic radiation [eg, brain], consult AstraZeneca for exception to this rule: protocol therapy will need to be held prior to and during the radiation treatment.

Confirmation of progression guidelines is set for patient management and treatment decisions in clinically stable patients continuing to receive treatment at an initial RECIST 1.1-defined PD. In the absence of clinical progression, patients may receive treatment until confirmed radiological progression according to the criteria listed below.

An immediate prior RECIST 1.1-defined radiological PD would be considered confirmed if any the following criteria are met in the subsequent follow-up scan (acquired preferably at the next regularly scheduled imaging visit but no sooner than 4 weeks after the RECIST 1.1-defined PD scan):

- $\geq 20\%$  increase in the sum diameters of TLs compared with the nadir at 2 consecutive visits, with an absolute increase of at least 5 mm in sum of diameters compared to nadir (as per RECIST 1.1 definitions)

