- *and/or* significant progression (worsening) of NTLs at the follow-up scan timepoint compared with the immediate prior timepoint (as per RECIST 1.1 definitions)
- *and/or* additional (brand) new unequivocal lesions at the follow-up scan timepoint (as per RECIST 1.1 definitions)
- *and/or* significant progression (worsening) of pre-existing new lesions at the follow-up scan timepoint compared with the immediate prior timepoint (unique definition)

Note: In order to have confirmed radiological progression, there should be 2 consecutive assessments meeting the PD definition, the first PD by RECIST 1.1 and the second PD using the Confirmation of Radiological Progression criteria (above). If the first assessment fulfilling the PD definition by RECIST 1.1 is not confirmed, in the absence of significant clinical deterioration, then the patient may continue with imaging tumor assessments until the next PD by RECIST 1.1, which will also require a follow-up scan evaluated using the Confirmation of Radiological Progression criteria.

**If the first PD (by RECIST 1.1) is not confirmed by the immediate next scan, then the Investigator should not change the PD assessment of the first scan.**

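### The synopsis stops immunotherapy when target lesions progress after a confirmed response, but Sections 6.2 and 7.1 and Appendix F omit the rule, and Appendix F permits dosing to confirmed progression

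*Protocol*

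**What the plan says.** The synopsis first gives clinically stable patients a general permission to stay on treatment after a first RECIST 1.1 progression. It then limits that permission: patients "will not be permitted to continue immunotherapy if progression occurs after confirmed response". The limit applies when response and progression both occurred in the target lesions, on immunotherapy, within the same treatment period, whether or not new lesions have appeared.

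Appendix F (Confirmation of Radiological Progression) repeats the permission without the limit:

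- "Patients who are clinically stable at an initial RECIST 1.1-defined PD may continue to receive treatment at the discretion of the Investigator and patient".
- It introduces a closed list with "The criteria for continuing treatment despite RECIST 1.1-defined progression are as follows". The list has two entries: no clinically significant progression with declining performance status, and no rapid progression or threat to vital organs or critical sites. Neither concerns prior response.
- "In the absence of clinical progression, patients may receive treatment until confirmed radiological progression according to the criteria listed below".

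Footnote b of Table 5 tells sites where to look: "Refer to Section 6.2 for details on duration of treatment and criteria for treatment through progression (Appendix F"). Section 6.2 sets dosing "until confirmed PD as per RECIST 1.1 as assessed by the Investigator unless there is unacceptable toxicity" or another reason to stop applies. The patients it names as ineligible to continue are those with rapid progression, or with symptomatic progression needing urgent intervention. Section 4.2.3 treats until progression and loss of benefit, "or until another discontinuation criterion is met (see Section 7.1"). The progression entries in Section 7.1 are clinical progression and confirmed radiological progression.

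**The concern.** The synopsis removes the investigator's discretion for one group of patients, and Appendix F grants that discretion to the same group. A site that follows the protocol's own cross-references for treatment through progression never meets the exclusion. The same dosing decision is then a deviation under one section and compliant under another.

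What is at stake is exposure after progression in patients whom the synopsis excludes from further immunotherapy, and uneven handling between sites. This is a matter of conduct, with a modest patient-safety side. It does not concern the primary analysis.

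**Working it through.** **Where the exclusion appears.** The places that govern treatment past progression read as follows:

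- Synopsis, Progression during treatment: exclusion stated.
- Table 1 footnote b: continuation at discretion; no exclusion.
- Table 1 footnote q: treat to confirmed progression; no exclusion.
- Table 2 footnote j: continuation at discretion after consulting the sponsor; no exclusion.
- Section 4.2.3: points to Section 7.1 for other reasons to stop; no exclusion.
- Section 6.2: names two kinds of progression that rule out continuing; not this one.
- Sections 7.1 and 7.1.1: no exclusion.
- Appendix F: two continuation criteria; no exclusion.

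**Worked case.** A patient has a confirmed partial response in the target lesions. The target lesions then grow by at least 20% and 5 mm from the nadir, and the patient is clinically stable. Under the synopsis, immunotherapy stops at this first progression. Under Appendix F, the patient meets both continuation criteria and may be treated until the follow-up scan.

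**Extra exposure per patient.** Inputs:

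- Scans every 8 weeks to week 48, then every 12 weeks (Table 1): weeks 8, 16, 24, 32, 40, 48, 60, 72, 84.
- One cycle is 28 days, with one durvalumab infusion and 56 olaparib/placebo doses (Section 1.1).
- A response is confirmed at the next scheduled scan (Section 8.1).
- The follow-up scan after progression comes at least 4 weeks later and no later than the next scheduled visit (Appendix F).

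The earliest scheduled sequence is response at week 8, confirmation at week 16 and progression at week 24.

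Formula: cycles = (weeks from first progression to follow-up scan) / 4; doses = cycles × 56.

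- Progression at weeks 24 to 40: 8 / 4 = 2 cycles, so about 2 infusions and 2 × 56 = 112 doses.
- Progression at week 48 or later: 12 / 4 = 3 cycles, so about 3 infusions and 3 × 56 = 168 doses.
- Follow-up scan at the 4-week minimum: 4 / 4 = 1 cycle, so about 1 infusion and 56 doses.
- Progression at week 24 not confirmed at week 32, next progression at week 40 at the earliest, confirmatory scan at week 48: 24 / 4 = 6 cycles, so about 6 infusions and 6 × 56 = 336 doses.

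For the last case, Appendix F says only that after a non-confirming scan "then the patient may continue with imaging tumor assessments until the next PD by RECIST 1.1". Continued dosing in that interval rests on its separate permission to treat until progression is confirmed.

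All these counts assume no delay, interruption or earlier stop. They ignore the ±1 week window and unscheduled scans. None is a minimum, because Sections 7.1 and 8.4.5.2 allow earlier stopping and interruption.

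**Endpoints.** PFS is dated at the first RECIST 1.1 progression, and Appendix F says that assessment is not revised if the next scan fails to confirm it. ORR uses data up to progression, and DoR ends at the PFS event. None of the three depends on whether dosing continues afterwards.

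**The case against.** The strongest answer is that this is an exception stated once, not a contradiction. The synopsis is Section 1.2 of the protocol. Appendix F is permissive and never addresses prior responders, so the specific rule can be read as limiting the general one. A site that stops such a patient at first progression complies with every section. Section 6.2 also ends treatment when another discontinuation criterion applies, without tying that phrase to Section 7.1.

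Much of this is fair. Appendix F allows continuation and does not require it, so the conflict is between a prohibition and a permission. A reader holding both texts could reconcile them. The difficulty is that the protocol sends sites to Section 6.2 and Appendix F, not to the synopsis, and Section 4.2.3 sends them to Section 7.1. None of these carries the exception, so a site can follow every reference and still give dosing that the synopsis forbids.

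It can also be said that the protocol never presents the exclusion as a safety measure and that other safeguards apply to the same patients. These are the exclusion of rapid or urgent symptomatic progression, the toxicity check, mandatory stopping of both drugs at clinical progression and, in Table 2 footnote j, consultation with the sponsor. That stands and keeps the safety consequence modest, although Table 1 footnote b, which covers patients still on treatment, omits the consultation.

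Finally, the group is narrow. If the response rates that the protocol cites for checkpoint inhibitors in other urothelial studies (17% to 29%, Sections 2.2.1 and 2.3.2.1) applied here, 150 × 0.17 = 25.5 to 150 × 0.29 = 43.5, or about 26 to 44 patients, would respond. Only some would go on to target-lesion progression while clinically stable and on treatment. This is an assumption, not an estimate, since adding olaparib could raise the response rate.

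**Conclusion.** The point holds. The exclusion is in the synopsis only, and the sections to which sites are directed leave it out while Appendix F permits dosing to confirmed progression.

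Per affected patient, the excess is up to about 2 infusions (112 doses) or 3 infusions (168 doses), depending on when progression occurs. It reaches about 6 infusions (336 doses) in the one-non-confirmation sequence. All of this is conditional on uninterrupted dosing and nominal scan dates. The protocol gives no basis for counting affected patients.

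PFS, ORR and DoR are not affected, and no effect on OS is shown. The exclusion falls on both arms, since both receive durvalumab. It should be corrected because it decides who is dosed past progression, but it does not threaten the trial's conclusions.

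**What to change.** If the exclusion is intended:

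- Add it to the Appendix F criteria for continuing treatment and to the Section 6.2 list of patients not eligible to continue.
- Add it to Section 7.1 as a mandatory reason to stop.
- Note the exception in Table 1 footnotes b and q.
- State whether olaparib/placebo stops too. The synopsis names immunotherapy only, but Section 7.1 allows one drug to be stopped alone solely for treatment-related toxicity, which implies that both stop.

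If it is not intended, delete the sentence from the synopsis.

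Either way the cost is a few lines of amendment text, with no change to the analysis or sample size.
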